5.3.1.2. RSV RNA log₁₀ viral load plaque assay (exploratory endpoints)

Measurement	Formula
Log ₁₀ viral load actual values	Log ₁₀ of actual values as measured using a quantitative viral culture (plaque assay)
Log ₁₀ viral load change from baseline	Log ₁₀ of actual value – Log ₁₀ of baseline value

5.3.1.3. RSV clinical outcome

Measurement	Formula
Length of hospital stay (hours) [Time-to event]	
The time from treatment initiation to hospital discharge (=event) in hours.
 
Subjects who complete or withdraw from the study prior to the event will be censored at the date of completion or withdrawal. If the time is not available they will be censored at 12:00. In case of death the subject will be censored at the maximum observed number of hours until the occurrence of the event or censoring for all subjects achieving the event or being censored because of study completion or withdrawal.
 
(Date and time of event or censoring - date and time of first dose of study drug)/3600, rounded to one decimal.

Time to readiness for discharge (hours) [Time-to event]	
The time from study treatment initiation to readiness for discharge (= event) in hours, with readiness for discharge defined by the investigator.
 
Derivation similar as “Length of hospital stay”

Length of hospital stay since hospital admission (hours) [Time-to event]	
The time from hospital admission to hospital discharge (= event) in hours.
 
Derivation of censoring similar as “Length of hospital stay”.
 
(Date and time of event or censoring - date and time of hospital admission)/3600, rounded to one decimal

Measurement	Formula
Time to readiness for discharge since hospital admission (hours) [Time-to event]	
The time from hospital admission to readiness for discharge (= event) in hours, with readiness for discharge defined by the investigator.
 
Derivation similar as “Length of hospital stay since hospital admission”

Duration of intensive care unit (ICU) stay (hours) [Duration]	
The total number of hours a subject stayed in ICU (= event) from first intake until study termination, calculated as sum of [(end date and time of event - start date and time of event)/3600], rounded to one decimal for all separate events per subject
 
If the initial start time is prior to the first dose of study drug, the duration prior to the first dose of study drug will be deducted from the overall duration.
 
If the end date is missing, the end date is considered to be after study completion or withdrawal. If the end date and time is after the study completion/discontinuation, the duration after the date and time of study completion/discontinuation will be deducted from the overall duration. If the time is not available it will be put at 12:00.

Requirement for intensive care unit (ICU) stay	
Does the subject require admission to the ICU after first dose of study drug? Categories will be Yes (1) or No (0).
 
Only derive this parameter for subjects that were not in ICU before first dose of study drug.

Requirement for oxygen supplementation	
Does the subject require any oxygen supplementation (noninvasive or invasive) after first dose of study drug? Oxygen supplementation is indicated on the Oxygen Supplementation form: Type of supplemental oxygen administration.
 
Categories will be Yes (1) or No (0).
 
Only derive this parameter for subjects that didn't require oxygen supplementation before first dose of study drug.

Requirement for noninvasive nonmechanical ventilation	
Does the subject require noninvasive nonmechanical ventilation support after first dose of study drug? On the Oxygen Supplementation form, oxygen supplementation is

Measurement	Formula
support	
indicated but the type of supplemental oxygen administration doesn't equal "Non-Invasive Mechanical Ventilation" or "Invasive Mechanical Ventilation"?
 
Categories will be Yes (1) or No (0).
 
Only derive this parameter for subjects that didn't require oxygen supplementation before first dose of study drug.

Requirement for noninvasive mechanical ventilation support	
Does the subject require noninvasive mechanical ventilation support after first dose of study drug, as indicated on the Oxygen Supplementation form: Type of supplemental oxygen administration equals "Non-Invasive Mechanical Ventilation"?
 
Categories will be Yes (1) or No (0).
 
Only derive this parameter for subjects that didn't require noninvasive mechanical ventilation support or invasive mechanical ventilation support before first dose of study drug.

Requirement for invasive mechanical ventilation support	
Does the subject require invasive mechanical ventilation support after first dose of study drug, as indicated on the Oxygen Supplementation form: Type of supplemental oxygen administration equals "Invasive Mechanical Ventilation"?
 
Categories will be Yes (1) or No (0).
 
Only derive this parameter for subjects that didn't require invasive mechanical ventilation support before first dose of study drug.

Requirement for supplemental feeding/hydration	
Does the subject require supplemental feeding/hydration (e.g. IV catheter/nasogastric tube) after first dose of study drug?
 
Categories will be Yes (1) or No (0).
 
Only derive this parameter for subjects that didn't require supplemental feeding/hydration before first dose of study drug.

Time to end of intensive care	The time from first study drug intake until the time of

Measurement	Formula
unit (ICU) stay (hours) [Time-to event]	
discharge from the ICU after which the subject was not readmitted to the ICU (= event)
 
Subjects who complete or withdraw from the study prior to the event will be censored at the date of completion or withdrawal. If the time is not available they will be censored at 12:00. In case of death the subject will be censored at the maximum observed number of hours until the occurrence of the event or censoring for all subjects achieving the event or being censored because of study completion or withdrawal. If no admittance to the ICU was necessary, the value will be set to 0.
 
(Date and time of event or censoring - date and time of first dose of study drug)/3600, rounded to one decimal

Time to end of Oxygen supplementation (hours) [Time-to event]	
The time from first dose of study drug start of oxygen supplementation to the last end date and time of any oxygen supplementation (= event) in hours (Oxygen supplementation is indicated on the Oxygen Supplementation form: Type of supplemental oxygen administration.). (Note: it is not necessary that the subject started on oxygen at baseline.)
 
If the end date is missing, the end date is considered to be after study completion or withdrawal.
 
Subjects who complete or withdraw from the study prior to the event will be censored at the date of completion or withdrawal. If the time is not available they will be censored at 12:00. In case of death the subject will be censored at the maximum observed number of hours until the occurrence of the event or censoring for all subjects achieving the event or being censored because of study completion or withdrawal.
 
If no oxygen supplementation was necessary after first dose of study drug, the value will be set to 0 hours.
 
(Date and time of event or censoring - date and time of first dose of study drug)/3600, rounded to one decimal

Time to end of noninvasive mechanical ventilation support (hours) [Time-to event]	
The time from first dose of study drug to the last end date and time of noninvasive mechanical ventilation and invasive mechanical ventilation support (= event) in hours. Noninvasive mechanical ventilation and invasive mechanical

Measurement	Formula
	
ventilation are defined as indicated on the Oxygen Supplementation form: Type of supplemental oxygen administration.
 
Derivation similar as “Time to end of Oxygen supplementation”

Time to end of invasive mechanical ventilation support (hours) [Time-to event]
	
The time from first dose of study drug to the last end date and time of invasive mechanical ventilation support (= event) in hours. Invasive mechanical ventilation support is defined as indicated on the Oxygen Supplementation form: Type of supplemental oxygen administration.
 
Derivation similar as “Time to end of Oxygen supplementation”

Time to end of supplemental feeding/hydration (hours) [Time-to event]
	
The time from first dose of study drug to the last end date and time of supplemental feeding/hydration (e.g. IV catheter/nasogastric tube) (= event) in hours.
 
Derivation similar as “Time to end of Oxygen supplementation”

Time to return to pre-RSV disease level for respiratory rate (hours) [Time-to event]
	
The time from first dose of study drug until the time to return to pre-RSV disease level. The return to pre-RSV disease level occurs when the observed value of the parameter is indicated by the investigator as normal, and no later observed values are indicated by the investigator as abnormal (=event).
 
Normalization of respiratory rate (RR) will be derived from the answer to the corresponding question in the questionnaire “is this Respiratory Rate value normal for this patient?”
 
If no deterioration from pre-RSV disease levels occurred, the time will be set to time of first dose of study drug and the value will be set to 0 hours.
 
Subjects with an abnormal value at the last assessment will be censored at that time. Subjects for which this last assessment is the baseline assessment will be censored at time 0.

Measurement	Formula
	(Date and time of event or censoring - date and time of first dose of study drug)/3600, rounded to one decimal
Time to return to pre-RSV disease level for heart rate (hours) [Time-to event]	
Idem as Time to return to pre-RSV disease level for respiratory rate (hours) but for heart rate.
 
Normalization of heart rate (HR) will be derived from the answer to the corresponding question in the questionnaire “is this Pulse value normal for this patient?”

Time to clinical stability (hours) [Time-to event]	
The time from first dose of study drug until the time at which the each of the following criteria are met (=event):
 
 • Normalization of Oxygen supplementation (as in parameter Time to end of Oxygen supplementation), • Normalization of feeding/hydration (as in parameter Time to end of supplemental feeding/hydration) , • Normalization of respiratory rate (as in parameter Time to return to pre-RSV disease level for respiratory rate), and • Normalization of heart rate (as in parameter Time to return to pre-RSV disease level for heart rate). 
In case any of the four components is censored, the time to clinical stability will also be censored at the first time-point of the censored component.
 
Subjects who complete or withdraw from the study prior to the event will be censored at the date of completion or withdrawal. If the time is not available they will be censored at 12:00. In case of death the subject will be censored at the maximum observed number of hours until the occurrence of the event or censoring for all subjects achieving the event or being censored because of study completion or withdrawal.
 
(maximum(Date and time of event criteria or censoring) - date and time of first dose of study drug)/3600, rounded to one decimal

Time to return to pre-RSV disease level for body temperature (hours), [Time-to event]	
The time from first dose of study drug until the time to return to pre-RSV disease level. The return to pre-RSV disease level occurs when the observed value of the parameter is within the normal range (=event).
 
If no deterioration from pre-RSV disease levels occurred, the

Measurement	Formula										
	
time will be set to time of first dose of study drug and the value will be set to 0 hours.
 
Subjects with an abnormal value at the last assessment will be censored at that time. Subjects for which this last assessment is the baseline assessment will be censored at time 0.
 
(Date and time of event or censoring - date and time of first dose of study drug)/3600, rounded to one decimal.
 
The normal ranges can be found in the table below:
 
  
 Measurement method	Normal temperature range	
   
 Rectal	36.6°C to 38°C (97.9°F to 100.4°F)	
 
 Ear	35.8°C to 38°C (96.4°F to 100.4°F)	
 
 Oral	35.5°C to 37.5°C (95.9°F to 99.5°F)	
 
 Axillary	34.7°C to 37.3°C (94.5°F to 99.1°F)	
  
	Measurement method	Normal temperature range	Rectal	36.6°C to 38°C (97.9°F to 100.4°F)	Ear	35.8°C to 38°C (96.4°F to 100.4°F)	Oral	35.5°C to 37.5°C (95.9°F to 99.5°F)	Axillary	34.7°C to 37.3°C (94.5°F to 99.1°F)
Measurement method	Normal temperature range										
Rectal	36.6°C to 38°C (97.9°F to 100.4°F)										
Ear	35.8°C to 38°C (96.4°F to 100.4°F)										
Oral	35.5°C to 37.5°C (95.9°F to 99.5°F)										
Axillary	34.7°C to 37.3°C (94.5°F to 99.1°F)										
Time to SpO ₂ ≥ 93% on room air (hours) [Time-to event]	
The time from first dose of study drug until the time of first SpO₂ measurement ≥ 93% on room air, and where no supplemental oxygen supplementation is given at or after this time point and where no value < 93% are measured after this time point.
 
Subjects with SpO₂<93% on room air or who are still on oxygen supplementation at the last SpO₂ assessment will be censored at the date and time of the last SpO₂ assessment.
 
If no oxygen supplementation was necessary post-baseline and the subject had SpO₂ measurement ≥ 93% on room air at baseline and all post baseline measurements, the value will be set to 0.
 
(Date and time of event or censoring - date and time of first dose of study drug)/3600, rounded to one decimal
										
Incidence of acute otitis media	Did the subject have acute otitis media after first dose of study drug (use high-level term “Middle ear infections and										

Measurement	Formula
	inflammations”)? Categories will be Yes (1) or No (0). Only derive this parameter for subjects that didn’t have acute otitis media before first dose of study drug.
Incidence of all-cause mortality	Did the subject die after first dose of study drug? Categories will be Yes (1) or No (0).

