Vital signs	X	bid	bid	bid	bid	bid	bid	bid	bid	bid	bid

Phase Day	Screening 0	Treatment Phase			Follow-up Phase ^a							
		1	2	3 to 6 ^b	7 ^c (+2 days)	8 to 9	10 (+2days)	11 to 13	14 (+2 days)	15 to 27	28 (±2 days) EoS	
Study Procedure^d												
Nasal Swabs ^q												
Mid-turbinate nasal swab (if non-intubated) or endotracheal sample (if intubated): RSV diagnosis confirmation, viral and bacterial coinfection ^r	X											
Mid-turbinate nasal swab (if non-intubated) or mid-turbinate nasal swab and endotracheal sample (if intubated): RSV viral load, viral resistance (genome sequencing), biomarker, and infectious RSV viral load (plaque assay) ^s		X ^t	X	X	X		X		X			X
Clinical Laboratory Assessments												
Blood sampling for hematology ^u	X		X		X				X			
Blood sampling for biochemistry ^u	X				X				X			X
Urinalysis ^v	X			X					X			
Pharmacokinetics ^q												
Blood sampling for pharmacokinetics	Day 1 to Day 2											
		Post Dose 1	Post Dose 2									
		0.25 - 2h	0.5 - 1h 7h (±4)									
Group X ^w :		X	(X) ^x		X							
Group Y ^w :		X		(X) ^x	X							
Ongoing Subject Review												
Prior and Concomitant therapy	X	X	X	X	X	X	X	X	X	X	X	X
Adverse events	X	X	X	X	X	X	X	X	X	X	X	X

Abbreviations: bid: twice daily; ECG: electrocardiogram; eCOA: electronic clinical outcome assessment; eCRF: electronic case report form; EoS: end of study; IDMC: Independent Data Monitoring Committee; LD: loading dose; MD: maintenance dose; PK: pharmacokinetic(s); Q4h: every 4 hours; Q8h: every 8 hours; RSV: respiratory syncytial virus; SpO₂: peripheral capillary oxygen saturation.

Footnotes:

- a. If a subject is discontinued from study drug, a follow-up visit will be scheduled 2 days (+2 days), 5 days (+2 days), 9 days (+2 days), and 23 days (± 2 days) after the last dose of study drug was administered. Assessments should be performed as indicated in the Time and Events Schedule, respectively for the Day 7, Day 10, Day 14, and Day 28 visit.
- b. The subject may be discharged after Day 2 study procedures, but may also remain hospitalized if deemed appropriate by the investigator. Hospitalization duration will not be extended solely for study purposes.
- c. If treatment duration is increased to up to 10 days, then all assessments performed on Day 7 will again be performed 1 day (+2 days) after administration of the last MD.

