9. STUDY EVALUATIONS

9.1. Study Procedures

9.1.1. Overview

The [Time and Events Schedules](#) summarize the frequency and timing of efficacy, PK, biomarker, medical resource utilization, health economic, and safety measurements applicable to this study. There are 2 [Time and Events Schedules](#): 1 schedule for subjects who are hospitalized (up to their hospital discharge); 1 schedule for subjects after they are discharged from the hospital. Repeat or unscheduled samples may be taken for safety reasons or for technical issues with the samples.

The eCOA device will be provided to the parent(s)/caregiver(s) at screening to record the parent(s)/caregiver(s) ratings of the severity of the subject's symptoms (PRESORS) (see [Attachment 5](#)). The parent(s)/caregiver(s) will complete the eCOA twice daily (in the morning and in the evening); after Day 14, eCOA will be completed once daily in the evening (at approximately the same time each day) until the end of the study for subjects who have been discharged from the hospital. Whenever possible, the same parent(s)/caregiver(s) should

complete the eCOA throughout the study. The first parent/caregiver assessment on Day 1 needs to be recorded predose, before the LD. If the screening assessment was performed less than 8 hours prior to the LD, the predose assessment does not need to be performed. The first postdose parent/caregiver assessment must be performed between 6 and 12 hours after the LD (on Day 1 or Day 2, depending on the time of LD).

The investigator/study-site personnel will provide sufficient information to enable the parent(s)/caregiver(s) to complete the parent(s)/caregiver(s) eCOA and will ensure that the eCOA is completed correctly and on schedule to avoid missing or incorrect data.

Prior to completing the screening assessment, the parent(s)/caregiver(s) must complete a training module (included as part of the eCOA device) on how to enter responses to questions in the eCOA device. Study-site personnel will review the completion of the parent(s)/caregiver(s) eCOA on a daily basis.

The clinician eCOA ([Attachment 5](#)) will be completed by the investigator twice daily for the entire duration of hospitalization and once daily at the Day 7, Day 10, Day 14, and Day 28 visits during outpatient follow-up.

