Additionally, statistical modeling will be performed on the secondary endpoint of length of hospital stay, defined as the time from treatment initiation to hospital discharge in hours. Subjects for whom no timepoint could be established (eg, withdrawal of informed consent before reaching the endpoint) will be (right-)censored at the latest timepoint at which it could be established that the endpoint was not reached. The differences in length of hospital stay of active dose regimens versus placebo treatment will be estimated using the accelerated failure time model using appropriate contrasts; as baseline covariates stratification factors, absence/presence of other viral or bacterial infections, and baseline \log_{10} viral load will be added. Treatment effect versus placebo will be reported as acceleration factors including 95% confidence intervals. In case the model assumptions are not adequately met, appropriate sensitivity analyses will be performed as detailed in the SAP. For the secondary endpoint of length of hospital stay, defined as the time from study treatment initiation to readiness for discharge in hours, with readiness for discharge defined by the investigator, an analogous approach will be used. The length of hospital stay from admission to discharge and from admission to readiness for discharge (as defined by the investigator), measured in days, will be analyzed using an analogous approach. Analytical details will be provided in the SAP.

Analysis of the sequencing results of the L-gene or other genes (only if no mutations are seen in the L-gene) will be described in the SAP. Statistical analysis of the viral load, that may be generated with the plaque assay, will be described in the SAP.

Parent/Caregiver-reported Evaluation of Clinical Outcomes

Parent/caregiver-reported eCOA (PRESORS) will be descriptively summarized by treatment group and compared across treatment groups.

Clinician-reported Evaluation of Clinical Outcomes

Clinician-reported eCOA (PRESORS) will be descriptively summarized by treatment group and compared across treatment groups.

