- Floppy/lethargic/poor interaction
- Only responds to pain/unresponsive

7. Signs of increased work of breathing now

7.1. Does the subject show any of these signs of increased work of breathing now? (note all that apply)

- Subcostal retractions
- Intercostal retractions
- Tracheosternal retractions
- Tachypnea [*tachypnea needs defined within the system WHO values pop-up?*]
- None of the above [*cannot be checked if any other options selected*]

7.2. Does the subject show any of these signs of increased work of breathing now? (note all that apply)

- Nasal flaring
- Head bobbing
- Grunting
- Other signs of increased work of breathing not already reported
- None of the above [*cannot be checked if any other options selected*]

8. Does the subject show any signs of cyanosis?

- Yes
- No

9. Describe the subject's coughing now (select one)

- Little or no coughing
- Occasional strong cough, sometimes productive
- Frequent cough, sometimes causing choking, gagging, or vomiting

10. Describe the subject's nasal secretions now (select one)

- None
- Minimal, easily cleared with suctioning
- Moderate, but could be cleared with suctioning
- Extensive, requires frequent suctioning

11. Describe the subject's wheezing now (select one)

- No wheezing
- Terminal expiratory wheezing or only with stethoscope
- Entire expiration or audible during expiration without stethoscope
- Inspiration and expiration without stethoscope

12. Does the subject appear to be dehydrated now?

- Yes
- No

13. Do you have any concerns relating to the subject's overall condition? (select one)

- No concerns (condition is stable or improving)
- Some concerns (may become unstable/requires close observation)
- Extremely concerned (unstable, requires immediate medical review)

14. Overall, how would you rate the subject's current health status? (select one)

- Excellent
- Good
- Fair
- Poor

During hospitalization only:

15. Based on the clinical status of the subject, is the subject ready to be discharged?

- Yes
- No

At the Day 7 visit only (only for studies in which study drug is administered):

16. In general, was the oral dosing of the study medication well tolerated by the subject?

- Yes
- No

17. Study drug administration

17.1 During study drug administration, were any of the following reported? (note all that apply)

- Disgusted expressions after tasting medicine
- Cried after tasting medicine
- Refused (would not open mouth or turned head away to avoid medicine)

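### Time to readiness for discharge: a child sent home without a recorded readiness *Yes* is, read literally, censored at study completion (about 648 h) instead of at the last known *not ready* time

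*SAP*

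**What the plan says.** SAP 5.3.1.3 defines time to readiness from first dose, "with readiness for discharge defined by the investigator". It gives the endpoint no censoring rule of its own, only "Derivation similar as “Length of hospital stay". The length-of-stay row states: "Subjects who complete or withdraw from the study prior to the event will be censored at the date of completion or withdrawal". Deaths are placed at the longest observed time. Readiness measured from hospital admission takes over the same rule.

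Protocol Attachment 5 holds the only readiness field shown in either document, clinician item 15: "Based on the clinical status of the subject, is the subject ready to be discharged". It stands under an instruction limiting it to the hospital stay. Under Protocol 9.1.1 the clinician questionnaire "will be completed by the investigator twice daily for the entire duration of hospitalization". Footnote b of the in-hospital Time and Events Schedule adds: "The subject may be discharged after Day 2 study procedures". Footnote h has the caregiver complete the diary before the child leaves on the day of discharge. No matching footnote covers the clinician.

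Protocol 11.3 has a different rule. For length of stay, a child with no established event time is "right-)censored at the latest timepoint at which it could be established that the endpoint was not reached", and readiness is to be handled analogously.

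**The concern.** One censoring sentence serves two different kinds of endpoint. Discharge is an administrative fact known for every child, so a child without it at study completion really has been in hospital throughout. Readiness is a judgement recorded at intervals, and recording stops at discharge. A morning *No* followed by an afternoon discharge complies with the protocol, yet leaves a child who is at home, has no event and can no longer have one. Censoring that child at study completion asserts weeks of non-readiness that nobody observed and puts readiness later than discharge.

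The variable feeds the Kaplan-Meier, AFT, logrank and Gehan-Wilcoxon analyses and the viral-load quartile analyses in SAP 5.3.2.3. In SAP 5.4.2 it also stands in for duration of signs and symptoms.

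**Working it through.** The plan states no power or event count for this endpoint, so there is no figure to reproduce. The check has two parts.

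**1. What the rule does to one child.** SAP 2.5 sets Day 1 as the date of first dose. Under Protocol 10.1 a child completes the study at the last follow-up visit, Day 28 ± 2.

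- Day 28: (28 − 1) × 24 = 648 h. Window: (26 − 1) × 24 = 600 h to (30 − 1) × 24 = 696 h.
- Example: first dose Monday 10:00, last item-15 answer *No* on Wednesday 08:00, discharged Wednesday 16:00.
- Length of stay: event at 54 h.
- Readiness, SAP rule: censored at about 648 h, which is 648 − 54 = 594 h (about 25 days) after discharge.
- Readiness, Protocol 11.3 rule: censored at 46 h.

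**2. What it does to the analysis.** The AFT model is log T = μ + β·treatment + σε, with acceleration factor exp(β). Only the 60 per arm comes from the documents. Assumptions: log-normal readiness time, placebo median 84 h, σ = 0.6, true factor 0.75, and a share of children with no recorded *Yes*, unrelated to their readiness time and censored at 648 h.

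The model should expect almost nobody beyond 648 h: z = ln(648/84)/0.6 = 2.043/0.6 = 3.41, upper tail about 0.0003, or 60 × 0.0003 ≈ 0.02 children per arm. At 10% without a *Yes* there are 60 × 0.10 = 6. The fit absorbs them by raising the scale and the median.

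SAP 5.3.2 chooses among log-normal, log-logistic and Weibull by AIC. With that step included:

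| No recorded *Yes* (both arms) | Power, two-sided 5% | Fitted placebo median |
|---|---|---|
| 0% | about 72% | 84 h (assumed) |
| 5% | about 63% | about 90 h |
| 10% | about 43% | about 95 h |
| 20% | about 22% | about 125 h |

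The estimated factor stays close to 0.75 throughout. A repeat with another seed agreed within about five percentage points of power. Treatment was the only covariate; the SAP model also has stratification factors.

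Other planned analyses in the same setting:

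- Gehan power: 71% with none missing, 65% at 5%, 53% at 10%.
- Logrank power: 61% with none missing, 29% at 10%.
- Kaplan-Meier placebo median: about 92 h at 10% and 104 h at 20%.

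Unequal shares with no true effect (10% placebo, 20% active): estimated factor about 1.22, rejection about 20% at nominal 5%.

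**3. What the alternatives do.** A separate log-normal run assumed a placebo median of 72 h, discharge 0 to 12 h after readiness and a true factor of 0.75:

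| No recorded *Yes* | SAP rule | Censor at last *No* | Discharge as event |
|---|---|---|---|
| 5% | 53% | 74% | 76% |
| 10% | 29% | 71% | 77% |
| 20% | 18% | 68% | 72% |

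With none missing, power was 73%. At 20% missing the fitted placebo median was 127 h, 81 h and 74 h under the three rules. Censoring at the last *No* recovers most of the loss. It leaves the median slightly high because that censoring is informative: the child went home soon afterwards.

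**The case against.** The SAP says the derivation is similar, not identical, and asks to be read together with the protocol. A programmer following both might never reach 648 h. Neither document names item 15 as the sole source of readiness, and discharge could be taken as evidence of it. This stands as a reason to call the point a conflict to reconcile. It does not remove it: the SAP offers no other rule for readiness, and reading two conflicting rules together does not choose between them. Elsewhere in 5.3.1 the SAP censors assessment-based endpoints (time to undetectable virus, respiratory rate, temperature, SpO₂) at a last assessment.

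The size is also open. Twice-daily completion and the eCOA monitoring in Protocol 17.6 should keep missing entries few, though they cannot prevent a *No* before same-day discharge. At 2% missing there is almost no loss (AIC-selected power 71%, Gehan 73%). A log-normal fit without the AIC step looks worse, for example 36% power at 10% missing and 28% null rejection under the 10% versus 20% imbalance. The planned selection would usually choose log-logistic there, so those figures should not be quoted for the planned analysis.

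A reader might infer two stronger things. One is that the treatment effect is biased towards none; with equal missingness the factor hardly moves. The other is that the rule creates a false effect. That needs unequal recording between arms. The trial is double-blind, and faster discharge on active drug cannot be the cause when there is no effect. The documents give no reason to expect it under the null.

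Finally, length of stay is analysed alongside and is unaffected, and the number censored is tabulated, so the anomaly might be noticed.

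**Conclusion.** The point holds as an inappropriate censoring rule that conflicts with Protocol 11.3. Read literally, it gives an impossible result for any completer discharged without a recorded *Yes*. Withdrawals are censored at withdrawal, so the 648 h figure is for completers.

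The consequence is lost precision and inflated medians. Under the stated assumptions, AIC-selected power drops by about 9, 29 and 50 percentage points (72 − 63, 72 − 43, 72 − 22) at 5%, 10% and 20% missing. The share missing is assumed, and the actual loss scales with it. Bias in the treatment comparison is conditional on unequal recording and is not established.

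This should be fixed. It concerns secondary endpoints and the exploratory analyses built on them; the viral-load primary analysis is untouched.

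**What to change.** Before unblinding, give both readiness endpoints their own derivation in SAP 5.3.1.3:

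- Name the data source (clinician item 15) and say whether the first or a sustained *Yes* is the event.
- Replace censoring at study completion with the Protocol 11.3 rule: censor at the last in-hospital assessment showing not ready.
- Preferably, when a child is discharged with no recorded *Yes*, count discharge as the event, or interval-censor between the last *No* and discharge. Run the other approach as a sensitivity analysis. This goes beyond the protocol rule and is a choice to be written down in advance.
- Report by arm how many children were discharged without a *Yes*.

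The cost is SAP wording and a change to the derivation program; discharge times and item-15 answers are already collected. After unblinding, the same change would be post hoc.
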